# 1.2.4 Clinical trial experience using cabotegravir plus rilpivirine as a dual antiretroviral therapy regimen in adolescents

IMPAACT 2017, also known as More Options for Children and Adolescents (MOCHA), is an ongoing Phase I/II, multi-center, open-label, non-comparative study to confirm the dose and evaluate the safety, tolerability, acceptability, and PK of oral CAB, long-acting injectable CAB (CAB LA), and long-acting injectable RPV (RPV LA) in adolescents aged 12 to less than 18 years, living with HIV who are virologically suppressed, and weighing at least 35 kg. CAB LA + RPV LA is approved for treating virologically suppressed adolescents living with HIV who are 12 years of age or older and weighing over 35kgs by the US Food and Drug Administration (FDA) based on data from adult and MOCHA studies.

Preliminary data from the MOCHA study are described below. At the time of the analysis, a total of 23 participants were enrolled: eight participants having received oral CAB followed by CAB LA (Cohort 1C), and fifteen participants having received oral RPV followed by RPV LA (Cohort 1R). There were two premature treatment discontinuations: one due to urticaria, assessed to be an acute allergic reaction related to study product following first RPV dose, and one due to excessive pain with needle insertion (13).

Acceptability among 21 virologically suppressed adolescents enrolled in the MOCHA trial was generally favorable(14). The desire to avoid taking daily pills and difficulty taking daily pills was the major (76.2%) reason for enrolling into the study. Eleven adolescents and 11 caregivers underwent

[figure not shown]
in-depth interviews. The themes reported from the interviews reiterated the difficulty with daily pills and expressed concerns with maintaining long-term adherence to routine injection schedules.

[figure not shown]
Preliminary PK data from MOCHA found that CAB LA and RPV LA when given individually, in conjunction with background ART, achieve PK targets in the enrolled adolescents living with HIV(13). The Cohort 1C median CAB (oral and IM) PK parameters were within the desired median PK target ranges: Cohort 1C Week 2 Oral median (range) CAB AUC0-τ: 160 (94.3-325) mcg\*h/mL (target median 46-277 mcg\*h/mL), Week 16 IM median (range) CAB trough: 3.11 (1.22-6.19) mcg/mL (target median 0.71-6.7 mcg/mL). Similarly, the Cohort 1R median RPV PK parameter was within the desired median PK target range: Week 16 IM median (range) RPV trough: 52.9 (31.9-148) ng/mL (target for median 25-100 ng/mL).

Adult CAB and RPV LA Population (POP) PK models were developed utilising exposure data from adult clinical studies with efficacious dosing regimens having an acceptable safety profile with Q4W and Q8W injections. Simulations were conducted with these models, also considering any potential age and weight-related impact on PK, to recommend appropriate doses in adolescents that achieve comparable exposures to those seen in adults. Additionally, PK data from the first 16 participants enrolled to MOCHA were compared against *a priori* population PK model predictions and agreed with the predicted exposure range and were within thresholds, as displayed in Figure 2, Figure 3, and Figure 4 for CAB and RPV. CAB and RPV exposures at other regimens (e.g., Q8W) in adolescent participants can also be predicted with these models, and based on the results from the model predictions, the MOCHA study has been updated to administer the Q8W regiment to all new participants. These models will inform the selection of the initial weight-band dosing regimens used in the CRAYON study.

# Figure 2. Observed preliminary IMPAACT 2017 Cohort 1C CAB concentrations in adolescents stratified by weight and age compared to model-predicted concentrations based on POP PK analyses from adult studies

Note: The plots represent the CAB systemic exposure: solid line and shaded band reflect the population pharmacokinetic model predictions (median and 90% interval) in the adults; the dots represent the observed individual adolescent data from MOCHA. The dashed lines represent the maximum observed geometric mean exposure from the TQT study at (22.5 mcg/mL) at supratherapeutic doses following 150 mg q12h x 3 and the target 5th percentile of the observed CAB trough concentration (0.45 mcg/mL) following the initiation injection in Phase 3 studies.

[figure not shown]

Figure 3. Observed IMPAACT 2017 Cohort 1R preliminary data and predicted RPV plasma concentrations in adolescents after PO RPV 25 mg once daily (left panel) and IM RPV LA 900-600-600 mg (right panel) Note: Black line and blue shaded area: median and 90% prediction interval for adolescents; black dots: observed data in Cohort 1R adolescents.

[figure not shown]
[figure not shown]

Figure 4. Observed trough RPV plasma concentrations in Cohort 1R adolescents (blue dots) and adults (boxplots, ATLAS/FLAIR) after PO RPV 25 mg once daily (Week 0; last day of PO lead-in), and IM RPV LA 900-600-600 mg (Weeks 4, 8 and 12; concentrations four weeks after injection)

# 1.2.5 Summary of safety data of CAB LA + RPV LA combination therapy

Overall, over 3000 participants have been exposed to oral and/or LA CAB + RPV during ViiV Healthcare-sponsored HIV-1 treatment clinical studies in Phase II/IIb and Phase III/IIIb (as of March 2022).

The integrated analysis of safety data across the Phase III clinical studies (Studies 201584 [FLAIR] and 201585 [ATLAS]), in combination with Phase I and Phase II data, supports an acceptable CAB + RPV safety profile. The following safety conclusions were drawn:

- The incidence of SAEs reported in FLAIR and ATLAS were comparable between CAB + RPV and the current antiretroviral regimen (CAR). Thirty-one (5%) participants in the CAB + RPV group and 26 (4%) participants in the CAR group had non-ISR SAEs. The most frequently reported SAE with CAB + RPV occurring in more than one participant was hepatitis A (n=4). A single SAE in the CAB + RPV treatment group was considered study drug-related by the investigator: an SAE of right knee monoarthritis.
- At the time of the pooled analysis, no fatalities were reported for participants receiving CAB + RPV during FLAIR and ATLAS. During Phase II studies, there were 5 fatalities. Only one death (myocardial infarction) was considered study drug-related (CAB + RPV) by the investigator. The participant had been on treatment for approximately 3 years and had several risk factors for cardiovascular disease.
- There were no cases of serious reactions such as drug-induced liver injury (DILI) or hypersensitivity reactions (HSR) in FLAIR and ATLAS with CAB + RPV. During Phase I and Phase II, DILI was identified in 5 participants receiving oral CAB (incidence was <1%). In FLAIR and ATLAS, there was a higher incidence of Grade 3/4 ALTs and participants who met Liver Stopping Criteria (LSC) in the CAB + RPV treatment regimen, which is due to the higher incidence of acute viral hepatitis occurring on the regimen.
- 'AEs of special interest' (AESI) have been determined for CAB + RPV (oral and IM) based on: non-clinical and/or clinical safety data for CAB and RPV (oral and IM); labelling and/or regulatory authority interest for approved INSTIs; and/or regulatory authority requirements. Results from the Phase III studies indicated that CAB + RPV appears to have no clinically relevant effect on safety related to the following AESI: QT prolongation, seizures, rhabdomyolysis, pancreatitis, or impact on creatinine.
- The rate of discontinuation was low overall for FLAIR and ATLAS. 22 (4%) participants in the CAB + RPV group and 9 (2%) participants in the CAR group had adverse events (AEs) leading to withdrawal/permanent discontinuation of study drug during the Maintenance Phase. The most common AEs leading to withdrawal with CAB + RPV were acute viral hepatitis (n=9) and ISRs (n=5). All individual AEs leading to withdrawal had an incidence of <1%.
- The most frequently reported adverse events (AEs) in the Phase III program were injection site reactions (ISRs), mainly ISR pain. ISRs were generally mild or moderate with no Grade 4 or Grade 5 or serious ISRs. 22 (4%) participants had Grade 3 ISRs, suggesting that ISRs generally did not interfere with daily activities. Most ISRs resolved within seven days. The percentage of participants reporting ISRs at each visit decreased over time. Few ISRs led to withdrawal.
- Other common AEs that were reported more frequently during treatment with CAB+ RPV in FLAIR and ATLAS were hemorrhoids, pyrexia, headache, dizziness, fatigue and back pain. Except for headache, the incidence of these AEs in the CAB + RPV group was <10%. Drugrelated AEs, as identified by the investigator, were reported with a higher incidence with CAB + RPV compared with CAR in FLAIR and ATLAS. The most common drug-related non-ISR AEs were headache, pyrexia, nausea, fatigue, asthenia, body temperature increased, myalgia, and dizziness. Most drug-related AEs were Grade 1, although a few Grade 3 and 4 AEs occurred. The most frequent drug-related Grade 3 and 4 AEs were pyrexia (4%), fatigue (3%), and asthenia (2%). Different frequencies of non-ISR, drug-related AEs between treatment groups may be expected for an open-label switch study where the comparator CAR group's participants had been on a stable and tolerable ART regimen.
- The incidence of neuropsychiatric events was low overall for suicidal ideation/behaviour, depression, and anxiety. Events occurred with similar frequency between treatment groups.
- The incidence of sleep disorder events (including drug-related events), particularly insomnia, was higher in the CAB + RPV group than that of the CAR group during the Phase III studies.
- No dose adjustment in CAB (oral or LA) or RPV (oral or LA) is required for patients with mild or moderate hepatic or renal impairment.
- Studies of co-administered oral RPV-25 mg and oral CAB-30 mg revealed no relevant drug interactions.

- The majority (74.7% CAB + RPV, 80.2% CAR%) of the maximum post-baseline emergent clinical chemistry abnormalities were Grade 1 or Grade 2 in intensity in pooled FLAIR and ATLAS. With the exception of creatine kinase and lipase, there were similar frequencies of Grade 3/4 clinical chemistry abnormalities between the treatment groups. No clinically relevant differences were observed overall in Grade 3 and Grade 4 post-baseline emergent abnormalities between the CAB + RPV and CAR groups.
- Results from FLAIR and ATLAS do not suggest any effect of age, sex, or race on the safety profile of CAB.
- Data from Study 207966 (ATLAS-2M) at the Week 48 analysis, showed the safety data from this randomized, open-label Phase III study of participants switching to Q8W CAB LA+ RPV is favorable and consistent with prior Phase II and III trials examining the Q4W and Q8W regimens.
- Preliminary safety data from the IMPAACT 2017/MOCHA study identified no new or unexpected safety issues or safety concerns and included all available safety data for the eight enrolled participants in Cohort 1C and the 15 enrolled participants in Cohort 1R (13). The safety data included in the analysis showed that in Cohort 1C, only one participant had a Grade 3 study product-related AE (insomnia on day 41 of study that resolved) but remained in the study. In Cohort 1R, only one participant had a Grade 3 study product-related AE (urticaria assessed to be an acute allergic reaction related to study product), resulting in permanent discontinuation of study treatment.

# 1.2.5.1 Summary of risks/side effects observed and/or monitored for in participants on cabotegravir + rilpivirine

The following risks have primarily been identified either during routine preclinical testing and/or from clinical trial experience in adults to date receiving CAB + RPV and are considered of potential relevance to clinical usage in the context of this protocol. Additional information about clinical experience to date and possible risks/adverse reactions associated with treatment using CAB and/or RPV can be found in the 'Summary of Data and Guidance for the Investigator' sections of the respective IBs for CAB and RPV.

#### Drug Induced Liver Injury (DILI) associated with CAB

A small proportion of participants in the CAB program to date have developed transaminitis (elevated liver transaminases characterised by predominant alanine aminotransferase (ALT) elevation). In most participants, transient transaminitis was explained by acute viral hepatitis infection (majority). In a small number of participants, there was not an alternative explanation, suggesting a mild form of drug induced liver injury (DILI) without hepatic dysfunction, which resolved upon withdrawal of treatment with CAB (15).

#### **Injection Site Reactions (ISRs)**

Clinical, experience to date has demonstrated that for adults, ISRs occur in the majority of exposed participants treated with CAB LA and RPV LA but are generally mild (Grade 1) or moderate (Grade 2) and include events of pain, tenderness, erythema, or nodule formation of several days' duration (median duration for individual events <1 week) (7).

ISRs may occur more than once in an individual participant receiving multiple injections. Although some Grade 3 ISRs were reported, overall ISRs have been well tolerated in adult participants and have not to date been associated with an excess of participants withdrawing.

#### **Hypersensitivity Reactions (HSR) (CAB)**

Hypersensitivity reactions have been reported as uncommon occurrences with this class of INSTIs, including the closely related compound dolutegravir, and were characterized by rash, constitutional findings, and sometimes, organ dysfunction, including liver injury (15).

While there have been no severe clinical cases of hypersensitivity reported to CAB to date, there is a theoretical risk of systemic or severe hypersensitivity reactions with or without hepatic symptoms associated with use of IM CAB (15). The long exposures anticipated after IM CAB injection may complicate the management of a drug hypersensitivity reaction, were it to occur.

#### Rash (RPV)

Some observations of rash with oral RPV have been reported in clinical studies executed to date (the majority are Grade 1 or 2) (16).

#### Effects in late-stage pregnancy observed in non-clinical studies with CAB

Nonclinical data from rat pre- and postnatal (PPN) studies have indicated reduced survival and viability rates amongst rat pups during the first 4 days of life at the maximum tested dose of 1000 mg/kg/day (maternal exposure). NOAEL was established at the mid dose 5 mg/kg/day, the maternal exposure at this dose calculated using systemic exposure from non-pregnant rats is >20 fold predicted Cmax and Area under the curve (AUC) exposures for anticipated clinical CAB LA exposures for HIV treatment.

In animal reproduction studies, CAB when administered to rats at >30 times the systemic exposure at the maximum recommended oral human dose (MRHD) of 30 mg during organogenesis through delivery, had adverse effects on labor and delivery that may be related to a delay in the onset of parturition, resulting in increased fetal mortality (stillbirths) and neonatal deaths immediately after birth.

The clinical significance in humans of these findings is unknown (15).

# Residual concentrations and risk of resistance following discontinuation of CAB LA or RPV LA

Residual concentrations of CAB and RPV can remain in the systemic circulation for prolonged periods (more than 1 year in some cases) in participants who stop CAB LA or RPV LA treatment (e.g., for tolerability issues or treatment failure) (7).

Participants discontinuing a CAB LA + RPV LA regimen may therefore be at risk for developing HIV-1 resistance to CAB and/or RPV after discontinuing injectable therapy (7).

#### **Drug-Drug Interactions (DDIs)**

For a complete listing of permitted and prohibited concurrent medications for CAB/CAB LA or RPV/RPV LA, refer to the IMPAACT 2036 Prohibited and Precautionary Medications listing in Appendix III.

# **Inadvertent Intravenous Injection (Accidental Maladministration)**

As with any intramuscular injection, it is possible that CAB LA or RPV LA can be inadvertently administered intravenously instead of intramuscularly possibly resulting in higher-than-expected concentrations of CAB or RPV shortly after injection and lower concentrations thereafter. This could

be due to administrator error, improper injection technique and / or improper needle length used based on body type.

# Post-injection reactions (RPV LA)

In clinical trials in adults, there have been occurrences of serious and non-serious post-injection reactions which were reported within minutes after the injection of RPV LA. Some of these events may have been associated with accidental partial intravenous (IV) administration of RPV during the intramuscular injection procedure, as suggested by pharmacokinetic (PK) assessments showing unexpectedly high plasma RPV concentrations post-dose. Symptoms ranged from mild to severe, with some participants receiving supportive care. These events have included symptoms such as dyspnea, bronchospasm, agitation, abdominal cramping, rash/urticaria, dizziness, flushing, sweating, oral numbness and, changes in blood pressure, and pain (e.g., back and chest). Symptoms typically began to resolve within a few minutes after the injection. These participants made a full recovery after the event resolved (16).

These events are infrequent and occurred in less than 0.5% of participants receiving repeat doses of RPV LA in clinical trials in adults. Of the symptomatic patients who had confirmed RPV PK elevations consistent with accidental partial IV administration, no patients had loss of virological control within weeks after the event (16).

#### Risk of Virologic Failure

This study employs a relatively novel 2 drug LA ART maintenance regimen for the treatment of HIV-1 infection. CAB LA + RPV LA have demonstrated antiviral activity in large clinical studies in adults and the two-drug combination has demonstrated sustained antiviral activity in studies LAI116482 (LATTE), 200056 (LATTE-2), 201584 (FLAIR), 201585 (ATLAS) and 207966 (ATLAS-2M) (7).

To limit the risk of virological failure and the chance of participants with archived NNRTI or INSTI resistance to be enrolled, virally suppressed participants on a stable oral ART regimen without prior evidence of NNRTI or INSTI resistance based either on prior HIV Drug resistance tests or clinical suspicion of prior resistance will be eligible for enrollment into this study.

Doses of CAB LA and RPV LA have been selected for this study, involving children, to achieve exposures that are expected to maintain virologic efficacy on the basis of available data with the oral and LA formulations in adults. Due to administration error, it is possible that a participant could receive an inadequate dose of CAB LA or RPV LA. Sub-therapeutic concentrations of either CAB LA or RPV LA could lead to virologic failure and possibly the development of viral resistance (7).

#### 1.3 Rationale

IMPAACT 2036 is a Phase I/II study to propose the weight-band dosing of oral cabotegravir (CAB) + oral rilpivirine (RPV) followed by long-acting injectable CAB (CAB LA) + long-acting injectable RPV (RPV LA) and assess the long-acting injectable regimen with and without an oral lead-in period in virologically suppressed children living with HIV-1, two to less than 12 years of age and weighing ≥10 kg and <40 kg. Both the European Medicines Authority (EMA) and United States Food and Drug Administration (FDA) have determined that the CAB LA + RPV LA regimen would not provide a significant therapeutic benefit over existing therapies in children less than two years of age and they will, therefore, not be included in the study population for IMPAACT 2036.

# 1.3.1 Rationale for the oral lead-in prior to injectable dosing in Cohort 1

The CAB LA and RPV LA formulations provide prolonged drug exposures, resulting from gradual release from the IM injection, that exposes the injected individual to detectable levels of cabotegravir and rilpivirine for up to 52 weeks or longer after an injection. An oral lead-in period of daily oral CAB and RPV prior to injectable administration, with serial safety assessments, can allow identification of any acute toxicity prior to administration of a non-dialysable, non-removable depot injection. A similar oral lead-in period was initially employed in previous trials in adults using these LA formulations. Throughout the course of the clinical development program for CAB LA and RPV LA, including the large Phase 3/3b trials FLAIR, ATLAS and ATLAS-2M, an oral lead-in phase of cabotegravir (30 mg) along with rilpivirine (25mg), administered daily for 30 days, was an integral component of these trials and allowed for a safety assessment before study participants were allowed to advance to the LA phase of these studies. As a result, all study participants underwent a one-month period of oral dosing with CAB/RPV followed by an evaluation of safety labs, and if labs were within normal limits, participants were allowed to transition into LA dosing. PK and safety data are necessary with the oral dosing to support labeling of an appropriate oral dose for children.

The oral lead-in period in Cohort 1 will provide uninterrupted study product coverage while awaiting the Week 4 safety laboratory test results, which will determine eligibility for receiving the LA formulations. The safety assessment is done towards the end of the 4-week oral lead-in and, for clarity, has been named the visit 4a. Safety lab results from the 4a study visit will be reviewed and, if appropriate, the next visit will be scheduled as soon as possible to administer the first study injections; this next visit has been named visit 4b. This nomenclature has been adopted to promote consistency across the CAB/RPV studies and allow for clearer interpretation and comparisons. Given a participant population with a history of durable viral load suppression at and prior to study entry, together with a viral load assessment at the 2-week visit, and questionable clinical meaningfulness of a single HIV-1 viral load blip, a repeat HIV-1 viral load assessment is not part of the laboratory assessments done at visit 4a to approve giving the first study injection at visit 4b. A HIV-1 viral load sample is collected at visit 4b to time with the first injections.

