*Note:* Participants undergoing dose modifications for growth or who have switched to a new formulation due to toxicity, tolerability, or changes in national treatment guidelines are considered eligible per this inclusion criterion. Treatment failure should be defined by local guidelines.

- **4.1.8** From a specimen collected less than six months (defined as within 179 days) prior to entry, has at least one of the following documented plasma HIV-1 RNA results:
  - <50 copies/mL, or
  - less than the lower limit of detection of the assay

- **4.1.9** From a specimen collected in the 6-18 months (defined as 180 to 545 days) prior to entry, has at least one of the following documented plasma HIV-1 RNA results:
  - <50 copies/mL, or
  - less than the lower limit of detection of the assay
- **4.1.10** At screening, a documented plasma HIV-1 RNA <50 copies/mL.

*Note:* HIV-1 RNA test results at screening cannot be used to satisfy inclusion criterion 4.1.8. If participant does not have a documented HIV-1 RNA test result at screening that satisfies 4.1.8, they should be referred for standard of care testing and return at a later date for screening.

- **4.1.11** Has normal, Grade 1, or Grade 2 results for all the following laboratory tests at screening (i.e., within 28 days prior to entry) based on grading per the Division of AIDS (DAIDS) Table for Grading the Severity of Adult and Pediatric Adverse Events:
  - **4.1.11.1** AST (<5.0 x ULN)
  - **4.1.11.2** ALT (<5.0 x ULN)
  - **4.1.11.3** Total bilirubin (<2.6 x ULN)
  - **4.1.11.4** Lipase (<3 x ULN)
  - **4.1.11.5** Estimated glomerular filtration rate (eGFR; ≥60 ml/min/1.73 m^2)
  - **4.1.11.6** Platelets ( $\ge 50,000 \text{ cells/mm}^3 \text{ or } \ge 50.00 \text{ x } 10^9 \text{ cells/L}$ )
  - **4.1.11.7** Hemoglobin (≥8.5 g/dL or ≥5.25 mmol/L)
  - **4.1.11.8** Neutrophils (≥600 cells/mm³)

*Note:* Laboratory tests may be repeated during the study screening period (i.e., within 28 days prior to entry), with the latest result used for eligibility determination. ALT and total bilirubin should also be assessed in consideration of Section 4.2.7.

- **4.1.12** Has no evidence of chronic hepatitis B infection based on hepatitis B surface antigen (HBsAg), hepatitis B core antibody (HBcAb), and hepatitis B surface antibody (HBsAb) testing at screening; any of the following three combinations of test results are acceptable for inclusion:
  - HBsAg negative, HBcAb negative, HBsAb negative

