- **4.2.7** Has the following combination of laboratory test results at screening (i.e., from specimens collected within 28 days prior to entry): ALT greater than or equal to 3 x ULN and total bilirubin greater than or equal to 1.5 x ULN and direct bilirubin greater than 35% of total bilirubin.
- **4.2.8** At entry, known active tuberculosis infection, as determined by the IoR or designee based on participant/parent/guardian report and available medical records.
- **4.2.9** At entry, any ongoing pancreatitis as determined by the IoR or designee based on participant/parent/guardian report and available medical records.
- **4.2.10** At entry, has symptoms suggestive of active coronavirus disease 2019 (COVID-19) or test results or contacts that require quarantine per local clinical practice, public health, and/or infection control guidelines as determined by the IoR or designee based on participant/parent/guardian report and available medical records.

*Note:* Potential participants with symptoms suggestive of active COVID-19, test results, and/or contacts that require quarantine may resume screening (or be re-screened) after symptoms have resolved and applicable quarantine requirements have been completed.

**4.2.11** Receipt of any prohibited medication within 7 days prior to entry, with the exception of antiviral agents that are part of the participant's ART regimen, as determined by the site investigator based on participant/parent/guardian report and available medical records, see Section 5.7.

*Note:* Medications and vaccines approved for emergency use (e.g., COVID vaccines) that do not appear in the IMPAACT 2036 Prohibited and Precautionary Medications listing are not exclusionary may be administered as per standard of care.

**4.2.12** Any past or current exposure to CAB LA or RPV LA

- **4.2.13** At entry, based on physical examination, has a current inflammatory skin condition that compromises the safety of intramuscular injections, as determined by the IoR or designee.
- **4.2.14** At entry, based on physical examination, has a dermatological condition overlying the buttock or upper thigh region, which, in the IoR or designee's opinion, may interfere with the interpretation of injection site reactions.
- **4.2.15** Enrolled in another clinical trial of an investigational agent, device, or vaccine.

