#### 4.3 Inclusion Criteria, Step 2: Continuation for Cohort 1 and Cohort 2a to injection phase

All participants enrolled in Cohort 1 or Cohort 2a will be assessed for eligibility to progress from the oral lead-in phase (Step 1) to the injection phase (Step 2), primarily based on the safety assessments from the Step 1 Week 4a study visit. Clinical assessments conducted prior to administering the first injection at the Week 4b visit will also be used to confirm eligibility to receive the injectable study product. See Sections 6.3.3 and 6.3.4 for Week 4a and Week 4b visit scheduling and order of procedures, respectively.

All of the following criteria must be met in order for a participant enrolled in Cohort 1 or Cohort 2a to be included in Step 2:

- **4.3.1** Currently enrolled as a participant in Step 1.
- **4.3.2** Has normal, Grade 1, or Grade 2 results from all of the following laboratory test results based upon specimens collected at the Week 4a study visit or from confirmatory repeat testing of Week 4a study visit laboratory tests:

```

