#### 8.1.6 Elevations in ALT or AST, Bilirubin

ALT, AST, total bilirubin, and direct bilirubin will be routinely monitored in this study.

In all cases of elevated ALT, AST, and/or elevated bilirubin (total or direct), possible alternative etiology should be assessed, and the underlying illness treated, or the likely causative agent removed. Sites should counsel participants and their parents/guardians about signs and symptoms of hepatotoxicity. Participants should be advised to notify the study site immediately if they develop any concerning signs or symptoms: new or worsening nausea, vomiting, unexplained loss of appetite; yellowing of the skin or eyes; increased weakness or fatigue; pain in the upper abdomen (liver tenderness or hepatomegaly); pale or clay-colored stools; and/or unexplained weight loss.

Elevated bilirubin in the absence elevated ALT or AST should be managed per Section 8.1.1.

ALT or AST results of severity grade 1 or 2 — other than the grade 2 results specified in the first two bullet points below — require no additional action. Study drug should be continued with routine monitoring per the Schedule of Evaluations unless more frequent monitoring is considered clinically indicated in the opinion of the site investigator. If any results of severity Grade 3 or higher are obtained, all four tests (i.e., ALT, AST, total bilirubin, and direct bilirubin) should be repeated as soon as possible and within three business days. Re-evaluation should continue at least weekly until improvement to grade 2 or lower or until stabilized and no longer in need of frequent monitoring, as determined by the site investigator and in consultation with the CMC.

Study drug must be held in the following scenarios (See Section 7.3.2 for EAE reporting requirements):

- Grade 2 ALT or AST with total bilirubin greater than two times the upper limit of normal (>2xULN) and direct bilirubin greater than 35% of total bilirubin. In this case, study drug should be permanently discontinued, and the CMC should be notified.
- Grade 2 or higher ALT or AST with signs or symptoms of clinical hepatitis (e.g., fatigue, nausea, vomiting, right upper quadrant pain, jaundice) or hypersensitivity (e.g., rash, fever, facial edema, eosinophilia, difficulty breathing). In this case, if another cause of the ALT or AST elevation is identified, consideration may be given to resuming study drug with approval from the CMC.

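### The Step 2 criteria omit the entry limits on total bilirubin, neutrophils and combined ALT/bilirubin, leaving two narrow patterns that bar entry but that no fixed rule stops before the first depot injection

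*Protocol*

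**What the plan says.** Section 1.3.1 explains that the oral lead-in "can allow identification of any acute toxicity prior to administration of a non-dialysable, non-removable depot injection". It adds that oral dosing covers the child while "awaiting the Week 4 safety laboratory test results, which will determine eligibility for receiving the LA formulations".

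At entry, Section 4.1.11 requires normal to Grade 2 results on eight tests. Two of them are "Total bilirubin (<2.6 x ULN") and "Neutrophils (≥600 cells/mm³"). Section 4.2.7 also excludes any child with "ALT greater than or equal to 3 x ULN and total bilirubin greater than or equal to 1.5 x ULN" when direct bilirubin exceeds 35% of the total. These criteria cover Cohorts 1, 2a and 2b.

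For Step 2, Section 4.3.2 asks for "Has normal, Grade 1, or Grade 2 results from all of the following laboratory test results" and then lists AST, ALT, lipase, eGFR, platelets, hemoglobin and CK. A note to that list sends a Grade 2 ALT to Section 8.1.6. Section 4.4 excludes children who have permanently stopped oral product (4.4.1), those with a related Grade 3 or higher event in Step 1 (4.4.2), and those the investigator considers unsafe to continue (4.4.3). Section 8.1.6 requires permanent discontinuation for "Grade 2 ALT or AST with total bilirubin greater than two times the upper limit of normal" with direct bilirubin above 35%.

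**The concern.** The Step 2 laboratory list is the formal barrier between the oral phase and an injection that cannot be removed. It repeats six entry limits unchanged, drops two, and has no counterpart to the combined liver criterion. No reason is given, although the Week 4a draw includes total and direct bilirubin and the absolute neutrophil count (Section 6.3.3).

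Cohort 2b makes the mismatch plainer. Those children receive the depot products at entry, so Section 4.2.7 applies before their first injection. Children in Cohorts 1 and 2a reach the injection after about four weeks on drug, and no equivalent criterion applies to their Week 4a results. Two liver standards therefore precede the first injection of the same products.

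What is at stake is participant safety, not precision or power. Drug-induced liver injury is the first CAB risk described in Section 1.2.5.1, where the cases without another explanation resolved once CAB was stopped. After a depot injection, drug can be detected for up to 52 weeks or longer (Section 1.3.1).

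**Working it through.** There is no sample-size calculation to reproduce. The check compares the two sets of criteria and then follows each omitted limit through the other rules.

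**Step 1: compare the criteria.**

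| Test | Entry (4.1.11, 4.2.7) | Step 2 (4.3.2, 4.4) | Drawn at Week 4a (6.3.3) |
|---|---|---|---|
| AST, ALT | <5.0 x ULN | same | yes |
| Lipase | <3 x ULN | same | yes |
| eGFR | at least 60 | same | yes |
| Platelets, hemoglobin | at least 50,000; at least 8.5 g/dL | same | yes |
| Total bilirubin | <2.6 x ULN | not listed | yes |
| Neutrophils | at least 600 | not listed | yes |
| ALT at least 3 x ULN + total bilirubin at least 1.5 x ULN + direct >35% | excluded | no counterpart | yes |

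CK is new in Step 2 and is left out of the comparison.

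**Step 2: cases that other rules stop.**
- Grade 3 or higher bilirubin or neutrophils assessed as related: Section 7.2 records Grade 3 or higher laboratory-only results as adverse events, so 4.4.2 bars Step 2.
- The combined pattern with total bilirubin above 2 x ULN: 8.1.6 requires permanent discontinuation, and 4.4.1 then bars Step 2.
- ALT of 5 x ULN or more: fails 4.3.2.2.
- Grade 2 or higher ALT or AST with signs of hepatitis or hypersensitivity: held under 8.1.6.
- Grade 4 of any cause managed under 8.1.1: held until the Clinical Management Committee (CMC) advises.

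**Step 3: cases that no fixed rule stops.**
1. *ALT 3 to <5 x ULN, total bilirubin 1.5 to 2.0 x ULN, direct >35%, no symptoms.* Entry excludes it (4.2.7). At Week 4a, ALT passes 4.3.2.2 and bilirubin is not a listed test. The 8.1.6 combination rule starts only above 2 x ULN, and other Grade 1 or 2 ALT results continue on drug. By the protocol's own limits (ALT <5.0, bilirubin <2.6 x ULN) neither value is above Grade 2, so 4.4.2 does not apply even if the change is drug-related. The gap is the interval from 1.5 to 2.0 x ULN between the two bilirubin thresholds.
2. *Grade 3 isolated bilirubin, or Grade 3 neutrophils, assessed as not related.* Entry excludes both (4.1.11.3, 4.1.11.8). Section 8.1.6 sends isolated bilirubin to 8.1.1; neutrophils have no section of their own and also fall under 8.1.1. That section continues product for an unrelated Grade 3, with weekly re-evaluation and CMC consultation if there is no improvement within two weeks. The same unrelated Grade 3 in ALT, AST, lipase, eGFR, platelets or hemoglobin bars injection, because 4.3.2 applies whatever the attribution.

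The two-week consultation need not come before the injection. Appendix II puts Week 4a at a target of day 28 and Week 4b no later than day 42. So 42 - 28 = 14 days is the longest interval from an on-target Week 4a, and Section 3.3 asks for it to be kept short.

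**Step 4: size.** The documents give no rate for these patterns. For an assumed per-child rate p, the chance of at least one case among n children is 1 - (1 - p)^n.
- p = 1%: 1 - 0.99^50 = 0.39 and 1 - 0.99^70 = 0.51. These match the protocol's Table 8.
- p = 0.5%: 1 - 0.995^50 = 0.22 and 1 - 0.995^70 = 0.30.

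**The case against.** The strongest reply is that Step 2 is more than its laboratory list, and that the rules in Step 2 of the working stop most of what matters. That is correct. A reader might infer from the missing limits that children with clear drug toxicity would go on to be injected. The documents do not support that: related Grade 3 events, the combined pattern above 2 x ULN, symptomatic hepatitis and Grade 4 results are all barred or held.

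Second, further safeguards exist. Section 8.1.6 asks for alternative causes to be assessed in every case of raised liver tests and sets repeat testing for Grade 3 or higher results. Section 6.9 requires the previous visit's laboratory results to be reviewed before any injection. Section 8.4 defers dosing for conditions judged unsafe, and 4.4.3 leaves room for judgment. These stand, but they are not fixed limits. Section 6.9 looks for reasons to hold or stop under Sections 8.4 and 8.5, which lead back to the 8.1 thresholds; the others rest on opinion. Entry has a similar discretionary clause (4.2.16) and still fixes numerical limits.

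Third, continuation criteria need not copy entry criteria. QTc and hepatitis B are not repeated either, and the note under 4.3.2 shows that a Grade 2 ALT was routed to 8.1.6 on purpose. This is a fair point, and a deliberate difference is possible. But no reason is stated, six limits are carried over unchanged, and 8.1.6 uses a higher bilirubin threshold than 4.2.7.

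Fourth, the second gap concerns only results judged not related, so it does not conflict with the purpose stated in Section 1.3.1. That is accepted: the rationale is not wrong. The inconsistency lies in 4.3.2 and 4.4 set against 4.1.11 and 4.2.7.

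**Conclusion.** The point holds in a limited form. The Step 2 and entry criteria disagree on three items measured at Week 4a, and after all other fixed rules are applied two patterns can still reach the injection. The first matters more because it applies even when the change is drug-related and because it would bar a Cohort 2b child from the same products. The second depends on the site assessing a Grade 3 result as not related.

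A case in this trial is plausible rather than expected. At assumed rates of 0.5% to 1%, the chance of at least one is 22% to 39% in 50 children and 30% to 51% in 70. No figure in the documents supports a particular rate, and lower rates give lower chances. The grade boundaries used are only those printed beside the protocol's own limits.

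A reader might also infer that later events in such a child would be attributed to the injectable and distort the safety results. The documents do not support this. The Week 24 primary safety analysis covers the oral and injectable phases together (Section 9.6.1.2), and relatedness is judged against all study agents (Section 8.1).

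**What to change.** Reconcile Sections 4.3, 4.4 and 8.1.6 with 4.1.11.3, 4.1.11.8 and 4.2.7 for the Week 4a results already drawn, so that one consistent standard precedes the first injection in Cohorts 1, 2a and 2b. If a difference is intended, state it in 4.3 with the reason. Which limits apply is for the sponsor's medical team to decide.

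The cost is a few lines of protocol text and an edit to the Step 2 eligibility checklist. No new test or visit is needed. Depending on the decision, a very small number of children may not proceed to injections.
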